Hypothesis 1: Post-ketamine rs-fMRI data will demonstrate a pattern of increased global brain connectivity (GBC) in fronto-temporal cortex.
- **Aim 2:** To examine the relationship between ketamine-induced glutamate alterations and changes in rs-fMRI of healthy subjects.
Design: Using MRS we will measure alterations in glutamate levels during ketamine infusion and correlate this data to rs-fMRI changes.
Hypothesis 2: Ketamine-induced glutamate alterations will positively correlate with changes in GBC.
- **Aim 3:** To examine the effect of administering a glutamate release inhibitor, lamotrigine, prior to ketamine infusion on neural network configuration and connectivity.
Design: Participants will be randomized to receive 300 mg oral lamotrigine or a matched-placebo medication 2-hours prior to ketamine infusion.
Hypothesis 3: Lamotrigine will attenuate the effect of ketamine-induced GBC enhancement in the neural network.

2. **Background:** Describe the background information that led to the plan for this project. Provide references to support the expectation of obtaining useful scientific data.

Ketamine

Major Depressive Disorder (MDD) is a leading cause of disability worldwide ¹, with a 21-fold increase of suicide attempts during major depressive episodes ². In the United States, the estimated lifetime prevalence is approximately seventeen percent ³. While more than 20 antidepressant medications are currently available, the efficacy of these medications is limited ⁴⁻⁷. Moreover, traditional antidepressants, all of which target the monoaminergic system, take weeks to months to reach their full clinical effects ⁸. Hence, there is an urgent need for a novel class of antidepressants that can offer (1) rapid acting effects and (2) efficacy in patients not achieving adequate benefit from existing medications. Over the last decade, accumulating evidence has shown that low dose of ketamine, a *N*-methyl-D-aspartate (NMDA) receptor antagonist, may possess both of these properties ⁹.

NMDA receptor dysfunction has been implicated in the pathophysiologic processes of depression, schizophrenia, and other psychiatric illnesses ^{10,11}. Ketamine is now the prototype for a new generation of antidepressants that rapidly alleviates depression and demonstrates efficacy even in patients with symptoms that are refractory to currently available treatments. The association between glutamate alterations and psychotomimetic effects of ketamine in human has been suggested

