proposal, we will implement state-of-the-art multi-modal neuroimaging methods to examine the role of ketamine-induced glutamate alterations on connectivity in rs-fMRI, the relationship between the alterations in connectivity and glutamate changes, and the impact of lamotrigine, a glutamate inhibitor. This will provide critical information concerning the impact of ketamine on neural connectivity and use of lamotrigine will allow us to confirm target engagement and the impact of blocking the glutamate system, furthering our understanding of the mechanisms of action and the role of glutamate in ketamine's effects. Moreover, given the well-characterized similarity between ketamine's acute psychotomimetic effects and psychosis ¹⁰, our ongoing studies are highly significant since the specific data generated with ketamine can equally contribute to the understanding and drug development of mood disorder and schizophrenia, devastating mental illnesses affecting millions of patients around the world ¹.

3. **Research Plan:** Summarize the study design and research procedures using non-technical language that can be readily understood by someone outside the discipline. Be sure to distinguish between standard of care vs. research procedures when applicable, and include any flowcharts of visits specifying their individual times and lengths. Describe the setting in which the research will take place.

A. Overview: In this study, 32 healthy participants will be randomized into one of two parallel groups: (a) open-label ketamine and active lamotrigine, or (b) open-label ketamine with a matched-placebo control (i.e., sugar pill). All participants will complete a baseline rs-fMRI approximately 1-week prior to the ketamine infusion and a follow-up rs-fMRI 24-hours post-infusion. The subanesthetic dose of ketamine (0.23mg/kg bolus followed by 0.58mg/kg infusion over approximately 60 minutes) will be administered via intravenous infusion to occur during the MRS scan. Participants will be administered lamotrigine (300 mg oral dose) or the matched-placebo control about 2-hours prior to the start of the infusion.

B. Experimental Subjects: Twenty-four healthy subjects between the ages of 21-65 years will be recruited for this study through advertising and referral from clinics in the community. Subjects will complete an informed consent process and will be thoroughly screened for inclusion and exclusion criteria as described below.

B.1. Restrictions

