Abbreviations: Big Five Inventory (BFI), Behavioral Inhibition & Activation Scales (BIS/BAS), Clinician Administered Dissociative States Scale (CADSS), Clinical Global Impression Severity/Improvement (CGI-S/I), Patient Global Impression-Severity/Improvement (PGI-S/I), Cogstate and brief neuropsychological battery comprises the cognitive testing portion, Columbia-Suicide Severity Rating Scale (C-SSRS), electrocardiogram (ECG), Early Trauma Inventory – Self Report (ETI-SR), Global Perceived Early-Life Stress (GPELS), Hamilton Anxiety Rating Scale (HAM-A), Klein Loss Scale (KLS), Life Events Checklist (LEC), Montgomery-Asberg Depression Rating Scale (MADRS), Modified Military Acute Concussion Evaluation (M-MACE), MGH Antidepressant Treatment Response Questionnaire (MGH-ATRP), Positive and Negative Symptom Scale (PANSS), Pittsburgh Sleep Quality Index (PSQI), Penn State Worry Questionnaire (PSWQ), Quick Inventory of Depressive Symptomatology – Self Report (QIDS-SR), Systematic Assessment for Treatment Emergent Events (SAFTEE), Structured Clinical Interview for DSM IV (SCID), Sheehan Disability Scale (SDS).

¹H-MRS Methods: ¹H-MRS will be used to measure glutamate concentrations in the frontal cortex using tissue segmentation processing to control for difference in tissue composition between subjects. Participants may be asked to return for one repeat session due to inadequate image acquisition or time constraints. This repeat session would be scheduled a minimum of 4-weeks after the original session to minimize carry-over effects and to minimize any potential risk from repeat dosing of ketamine or lamotrigine. No more than one repeat session would be conducted. A brief description of the methods is provided below.

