An 8-channel RF array (7.0 T magnet) will be used for RF transmission and signal reception. In the frontal cortex, the volume of primarily gray matter will be selected as a rectangular box placed across the anterior cingulate. The frontal white matter voxel will have identical dimensions offset from the midline. The sequence will be applied in pairs⁹⁶ to yield sub-spectra that contain either macromolecules alone or macromolecules combined with the metabolites of interest. Briefly, one sub-spectrum is acquired with a hyperbolic secant inversion pulse applied across the spectral bandwidth, followed by an inversion-recovery delay to null the metabolites, and one sub-spectrum is acquired without the inversion pulse. The macromolecules will be measured directly from the metabolite-nulled sub-spectrum. The macromolecule sub-spectrum will be subtracted from the other sub-spectrum to obtain a spectrum of metabolites alone. The data will be acquired in interleaved fashion, toggling between individual inverted and uninverted acquisitions, in short blocks. Each block will be stored, and the sequence will run for about 20-minutes to yield pairs of sub-spectra. Experience has shown that over 90% of subjects are able to lie still and tolerate this duration of scan. A spectrum of the water in the voxel will be obtained using the same pulse sequence and TE with the water suppression disabled. Spectral fitting will be performed to quantify the metabolites, and all metabolite measurements will be reported not only based on comparisons to creatine but as ratios to the tissue water peak.

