The sample size (n=32) was selected based on previous reports¹³. fMRI processing and GBC analyses will be conducted as previously reported¹⁰⁰. A paired t-test will be conducted to examine the effects of ketamine on GBC (Aim 1). A linear mixed model will examine the effects of ketamine and ketamine-by-lamotrigine interaction on cortical glutamate levels. Delta glutamate (during infusion minus baseline) will be correlated with delta GBC (post infusion minus baseline) (Aim 2). A t-test will compare delta GBC between the lamotrigine and placebo groups (Aim 3). Similar analyses will be conducted to examine the effects of ketamine and lamotrigine on the secondary outcomes, i.e. gln level, gaba level, cortical thickness, subcortical ROIs volumes, fractional anisotropy and mean diffusion, and amygdala activation.

SECTION VI: RESEARCH INVOLVING DRUGS, BIOLOGICS, RADIOTRACERS, PLACEBOS AND DEVICES
--

If this section (or one of its parts, A or B) is not applicable, state N/A and delete the rest of the section.

A. DRUGS, BIOLOGICS and RADIOTRACERS

1. **Identification of Drug, Biologic or Radiotracer:** What is (are) the **name(s)** of the drug(s) biologic(s) or radiotracer(s) being used? Identify whether FDA approval has been granted and for what indication(s).

I. Ketamine has U.S. Food and Drug Administration (USFDA) approval as the only anesthetic for diagnostic and surgical procedures that do not require skeletal muscle relaxation. Ketamine is also indicated for anesthesia induction prior to the administration of other general anesthetic agents or to augment low potency anesthetics such as nitrous oxide.

II. Lamotrigine has U.S. Food and Drug Administration (USFDA) approval as an anticonvulsant. It is also indicated for use in bipolar disorder.

All protocols which utilize a drug, biologic or radiotracer **not** approved by, but regulated by, the FDA, or a radiotracer regulated by the RDRC, must provide the following information:

a. What is the Investigational New Drug (IND) **number** assigned by the FDA?

Not applicable.

b. Who holds the IND?

Not applicable.

c. All protocols which utilize a radiotracer not approved by, but regulated by the FDA must provide the IND number: _____

Alternatively, use of the investigational radiotracer may be under RDRC/RSC oversight: (check if appropriate) _____

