All participants will be compensated for their participation. Subjects will be paid \$40 for screening, \$60 for each MRI study (2 studies total), \$40 for each cognitive testing session (2 sessions total), and \$300 for ketamine infusion test day. Failed imaging studies will be repeated and subjects will be paid additionally for the repeated scan. If participation in the scans has already begun and must be cancelled before completion, then compensation will be based on involvement in the study at a rate of \$20 per hour. Reasonable transportation costs up to \$100 on the infusion day will be reimbursed. Receipts must be submitted.

Therefore, we anticipate the subject's total earning – if he/she participates in all sessions – is \$540. At the principal investigator's discretion, further subject payment may be made for travel, parking, lodging, food or transportation.

The debit cards will be offered through the YCCI OnCore ePayments system and will be our preferred payment option. Subjects will be informed that they will receive payment via a Bank of America pre-paid debit card. We will provide their name, address, and telephone number to the Bank of America for processing and their card will be related to their name and number. Their SSN or other information will not be provided. All compensation information will be discussed in the informed consent process.

3. **Costs for Participation (Economic Considerations):** Clearly describe the subject's costs associated with participation in the research, and the interventions or procedures of the study that will be provided at no cost to subjects.

The only costs associated with the study are transportation to and from appointments. All services and evaluations are provided free of charge.

4. **In Case of Injury:** This section is required for any research involving more than minimal risk.
- Will medical treatment be available if research-related injury occurs?
 - Where and from whom may treatment be obtained?
 - Are there any limits to the treatment being provided?
 - Who will pay for this treatment?
 - How will the medical treatment be accessed by subjects?

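### Does Aim 2 need a rule that delta glutamate and delta GBC come from the same infusion when an MRS session is repeated?

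*Combined protocol and SAP*

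**What the plan says.** Hypothesis 2 (Section V, 1) reads: "Ketamine-induced glutamate alterations will positively correlate with changes in GBC". Section V, 12 turns it into a correlation of two change scores: "Delta glutamate (during infusion minus baseline) will be correlated with delta GBC (post infusion minus baseline) (Aim 2". Neither place names a session or an infusion.

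Section V, 3.A fixes the timing of the GBC scans: "All participants will complete a baseline rs-fMRI approximately 1-week prior to the ketamine infusion and a follow-up rs-fMRI 24-hours post-infusion". Glutamate is measured in the MRS session in which ketamine is infused, and Section V, 3.F plans a single test day.

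The 1H-MRS Methods paragraph of Section V, 3 then adds an exception: "Participants may be asked to return for one repeat session due to inadequate image acquisition or time constraints". On its timing it says: "This repeat session would be scheduled a minimum of 4-weeks after the original session to minimize carry-over effects and to minimize any potential risk". The reason given, to "minimize any potential risk from repeat dosing of ketamine or lamotrigine", shows that the repeat is a second exposure and not just a rescan.

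The 3T scans have their own repeat rule in the Magnetic Resonance Imaging paragraph: at most three repeats, with no link to a second infusion. Table 2 lists no rs-fMRI visit around a repeat infusion. Section X, 2 adds, as a payment provision: "Failed imaging studies will be repeated and subjects will be paid additionally for the repeated scan".

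**The concern.** Read together, these sections let the two halves of one Aim 2 data pair come from different infusions. Suppose the spectra from the infusion day are unusable but the 24-hour rs-fMRI is good. After a repeat MRS session, delta glutamate belongs to infusion 2 and delta GBC to infusion 1.

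Such a pair does not show the relationship that Hypothesis 2 is about, because the GBC change was complete before the glutamate change was measured. Unless a person's glutamate response is fully reproducible between infusions, the pair also pulls the correlation toward zero. With no rule, the choice to keep, drop or replace the pair would be made after the data are in, in a correlation with at most 32 points.

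**Working it through.** **Timing.** The repeat comes at least 4 × 7 = 28 days after the MRS session it replaces. The 24-hour GBC scan therefore precedes the repeat infusion by at least 28 − 1 = 27 days, and the baseline GBC scan by about 28 + 7 = 35 days or more.

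**How many participants?** The documents give no repeat rate. The nearest figure is in the 1H-MRS Methods: "Experience has shown that over 90% of subjects are able to lie still and tolerate this duration of scan". Read as a failure rate, it would give 32 × 0.10 = 3.2 participants, or 32 × (1 − 0.9²) = 6.1 if a baseline run and an infusion run must both succeed independently. That reading does not hold, for four reasons:

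- The figure is about tolerating a scan of about 20 minutes. It is not a rate of unusable spectra or of repeat sessions.
- Inability to complete MR studies is listed in Section V, 3.B.2 as a ground for discontinuation, so some of these participants would leave rather than return.
- Baseline MRS is set up 45 minutes before ketamine starts. A baseline failure noticed in time could stop the session before any first infusion, leaving nothing to mismatch.
- Acquisition runs from 5 to 75 minutes. In 70 minutes up to three full 20-minute runs fit, so one bad run need not lose the session.

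Repeats for time constraints are not covered by the figure at all. So 3 and 6 are neither estimates nor upper bounds.

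**What would mismatched pairs do?** Section 12 gives no alpha, power or expected correlation, so there is no stated figure to reproduce. For illustration, assume a true same-infusion r = 0.5, two-sided 5% and n = 32. Let m pairs be mismatched, with correlation ρ × r, where ρ (assumed between 0 and 1) is the share of the correlation that survives across infusions.

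- Pairs kept: r_eff = r × (1 − m/n + ρ × m/n)
- Power: Φ(atanh(r_eff) × √(n − 3) − 1.96)
- Pairs dropped: same power formula with r = 0.5 and n − m

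No mismatch: atanh(0.5) × √29 − 1.96 = 0.549 × 5.385 − 1.96 = 1.00, power 84.1%.

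Six pairs kept, ρ = 0.5: r_eff = 0.5 × (1 − 0.1875 + 0.09375) = 0.453; 0.489 × 5.385 − 1.96 = 0.67, power 74.9%.

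Six pairs dropped: 0.549 × √23 − 1.96 = 0.549 × 4.796 − 1.96 = 0.67, power 75.0%.

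| Mismatched pairs | Kept, ρ = 0 | Kept, ρ = 0.5 | Kept, ρ = 0.8 | Dropped |
|---|---|---|---|---|
| 2 | 78.2% | 81.2% | 83.0% | 81.4% |
| 4 | 71.4% | 78.2% | 81.8% | 78.4% |
| 6 | 64.1% | 74.9% | 80.7% | 75.0% |
| 8 | 56.5% | 71.4% | 79.4% | 71.1% |

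A simulation of 200,000 draws per cell gives the same picture, within 2 percentage points: 85.3% with no mismatch and, with six pairs, 65.2% (kept, ρ = 0), 76.2% (kept, ρ = 0.5) and 76.7% (dropped).

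**Where the two rules break even.** With f = m/n, keeping scales the signal by 1 − f(1 − ρ), and dropping scales it by √(1 − f), which is about 1 − f/2. These are equal at ρ of about 0.5, whatever m is. Below that, dropping is better; above it, keeping is better. The documents say nothing about ρ.

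**Direction of error.** If glutamate and GBC change are unrelated, a mismatched pair is also uncorrelated in expectation. Keeping such pairs therefore dilutes a true effect but does not by itself create a false one.

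**The case for a change.** The strongest case for a change is that the protocol itself foresees the repeat, so it should also say how the repeat is analysed. A sentence would cost nothing in acquisition and would remove a choice made after the data are seen. The single test day in Section V, 3.F does not settle the matter, because the 1H-MRS Methods paragraph expressly provides for a further session.

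Much of this stands. Section 12 has no pairing rule, a cross-infusion pair is possible, and the two statements about test days do not match and should be reconciled as protocol wording. A clarifying sentence would do no harm.

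It does not amount to a fault in the plan. Section 12 names the infusion-day glutamate change and the post-infusion GBC change in one sentence, against a schedule with one infusion and both rs-fMRI scans placed around it. Same-infusion pairing is the natural reading, and no text prescribes the other. The payment sentence in Section X, 2 sets compensation; it is weak evidence about which scans are redone.

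Which spectra between 5 and 75 minutes form the infusion value is also left open. That affects every participant, is a separate matter of analytic detail, and does not bear on the pairing.

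**Conclusion.** The gap is genuine but small, and no change to the plan follows. No stated rule gives a wrong result. The plan is silent on a contingency that touches only participants with a repeat MRS session, a number the documents do not give and that may be zero. An analyst meeting such a case would see that the two changes belong to different infusions, analyse same-infusion pairs, and report how many participants had a repeat and whether adding them alters the result.

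Making exclusion the rule would also be a trade-off, not a clear gain: under the assumptions above it matches keeping the pairs at ρ of about 0.5, and loses power beyond that. All power figures rest on an assumed r = 0.5, an assumed ρ and assumed counts, and are illustrative only. They also take n = 32, whereas the aims, Section V, 3.B and Section V, 5 say 24. At n = 24 with no mismatch, power at r = 0.5 is 71.1%, a drop of 84.1 − 71.1 = 13.0 points. That is more than the 84.1 − 74.9 = 9.2 points lost with six mismatched pairs at ρ = 0.5.

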- The principal investigator of this study is qualified to serve as P.I. and has the support of the hospital for this research project.

YNHH HSPA Name (PRINT) and Signature

Date

SECTION V: RESEARCH PLAN

1. **Statement of Purpose:** State the scientific aim(s) of the study, or the hypotheses to be tested.

Ketamine is an anesthetic agent, recently found to exert a rapid and potent antidepressant effect in severely depressed patients. Mounting evidence indicates that a ketamine-induced surge in glutamate neurotransmission, particularly in the frontal cortex, plays a crucial role in the antidepressant and psychotomimetic effects of the drug. Our preliminary data also suggests ketamine has a normalizing effect on long-range neural dysconnectivity in Major Depressive Disorder (MDD), and that these changes in functional connectivity, as measured by resting state functional MRI (rs-fMRI), are related to the antidepressant effect of the drug.

A better understanding of the mechanism of neuropsychiatric effects of ketamine are critically important, as pharmacological modulation of these effects can assist in the development of new medications for the treatment of multiple psychiatric disorders including depression and schizophrenia. The aims of the current proposal are to provide insight into (a) the impact of ketamine on functional connectivity as measured by rs-fMRI; (b) the relationship between rs-fMRI alterations and ketamine-induced neurochemical changes in glutamate; and (c) to investigate the influence of a glutamate release inhibitor (i.e., lamotrigine) on these ketamine-induced neural alterations in healthy volunteers using safe, minimally invasive, state-of-the-art multi-modal neuroimaging and behavioral assessment. Further examination of the effects of ketamine-induced changes in neural connectivity as well as the impact of a pre-treatment dose of lamotrigine can provide key insight into the role of glutamate and the mechanism of ketamine's rapid antidepressant and perceptual effects and its influence on neural connectivity.

- **Aim 1:** To characterize the effects of a single, sub-anesthetic dose of ketamine in rs-fMRI in healthy subjects.
Design: Twenty-four healthy participants will be randomized into one of two parallel groups—ketamine+lamotrigine or ketamine+placebo—and will complete pre- and post-ketamine rs-fMRI.

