28. *Socio-demographic/General Information*: At intake, demographic data and medical history will be assessed with interviews and self-report forms that provide data on age, race, socioeconomic status, marital status, educational and

occupational levels, and significant medical history. These are adapted from previous diagnostic and clinical studies at this center.

D.3. Biochemical Analyses: 10 mL of blood are drawn for the analysis of ketamine levels. Plasma ketamine levels are ascertained via a gas chromatography-mass spectroscopy assay developed by [name] M.D. ⁹⁵.

E. *Lamotrigine Administration:* Subjects randomized to the active lamotrigine group will receive a 300 mg oral dose of the drug 2-hours prior to the start of the ketamine-infusion. Lamotrigine levels will be measured using commercially available radioimmunoassay kits.

A physician who is trained and has experience with lamotrigine and possible allergic and other adverse events will remain in attendance at all sessions that involve drug administration.

F. *Ketamine Administration:* Subjects will complete one test day. Following an overnight fast, IV lines will be inserted into the antecubital vein. They will receive ketamine (0.23mg/kg bolus followed by 0.58mg/kg infusion over approximately 60 minutes).

A physician who is trained and has significant experience with both ketamine and infusion studies will remain in attendance at all sessions that involve ketamine infusion. The subjects will also be attended by a nurse who will accompany them through the study sessions, from the insertion of bilateral cannulae for drug infusion and blood sampling, through to recovery following ketamine infusion.

Baseline Test Session (Test Session 1 Day-0)

- T -15 min: Urine toxicology; Urine pregnancy test (women only);
Breathalyzer; MRI Safety Data Sheet; Metal Detector
- T -0 min: rs-fMRI (and other imaging protocols on the 3T scanner)
- Post fMRI Brief neuropsychological battery

Test session 1 (Day #1)

- T -120 min: Vital signs *; Urine toxicology; Urine pregnancy test (women only); Breathalyzer; PSWQ, PSQI, MRI Safety Data Sheet; Metal Detector; Lamotrigine or matched-placebo control administration
- T-90 min: Intravenous lines started
- T -45 min: MRS setup and baseline scan
- T-0 min: Ketamine infusion begins (0.23mg/kg bolus followed by 0.58mg/kg infused over 60 minutes)
- T 5-75: MRS acquisition continues

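### Aim 3 compares raw change in GBC between arms with no baseline covariate; adjusting for the pre-drug scan would usually be more precise at almost no cost

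*Combined protocol and SAP*

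**What the plan says.** Section V, 12 (Statistical Considerations) gives the Aim 3 analysis in one sentence: "A t-test will compare delta GBC between the lamotrigine and placebo groups (Aim 3". The Aim 2 sentence just before it shows that delta is the raw difference between the two scans: "correlated with delta GBC (post infusion minus baseline) (Aim 2". No covariate is named for the arm comparison there or elsewhere. The only model in the section is a linear mixed model, and it is for glutamate.

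Section V, 3.A sets the scan times: "All participants will complete a baseline rs-fMRI approximately 1-week prior to the ketamine infusion and a follow-up rs-fMRI 24-hours post-infusion". The visit schedule in Section V, 3.F also puts the baseline 3T session ahead of the dosing day.

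The MRS measures differ. On the dosing day the tablet is given at T -120 min and the schedule then lists "T -45 min: MRS setup and baseline scan", so that baseline is taken after lamotrigine or placebo.

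The planned total is inconsistent. Section V, 3.A says "32 healthy participants will be randomized into one of two parallel groups", and Section V, 12 and Section VII, 1 also use 32. Aim 1 in Section V, 1 says "Twenty-four healthy participants will be randomized into one of two parallel groups", and Section V, 3.B and Section V, 5 also use 24.

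**The concern.** A change score removes baseline with a coefficient fixed at 1. That is the best choice only when rho x SD(follow-up)/SD(baseline) equals 1. If the product is below 1, subtraction over-corrects and carries noise from the baseline scan into the outcome. Estimating the coefficient avoids this, at the price of one degree of freedom.

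Aim 3 is the only stated GBC comparison between the randomised arms, and the trial has 32 participants at most. Buying precision through recruitment would mean more healthy volunteers, each with a ketamine infusion, a 7T session and two 3T scans. Adjustment uses scans that are already planned.

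**Working it through.** **The plan's own figure.** Section V, 12 says "The sample size (n=32) was selected based on previous reports". It gives no alpha, power, effect size, SD, allocation ratio or dropout, so 32 cannot be reproduced. For scale only: with assumed two-sided alpha 0.05, 80% power and 1:1 allocation, 16 per arm detects 1.02 SD of the change score (noncentral t), and 12 per arm detects 1.20 SD.

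**Inputs.** N = 32, with 24 as a sensitivity case, both from the documents. The following are assumptions: 1:1 allocation, rho, and k = SD(follow-up)/SD(baseline), each taken as common to both arms, with normal data.

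**Formulas**, with the baseline SD set to 1 and the factor common to both methods dropped:

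- Change score: V_c = 1 + k² − 2·rho·k
- Baseline-adjusted: V_a = k²(1 − rho²) × [1 + 1/(N−4)]. The bracket is the average cost of estimating the slope: 29/28 = 1.036 at N=32 and 21/20 = 1.050 at N=24.

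**Worked case**, k = 1, rho = 0.5, N = 32: V_c = 1 + 1 − 1 = 1.000; V_a = 0.75 × 1.036 = 0.777. The ratio is 0.777, a 22% cut. A change-score test would need about 32/0.777 = 41 participants for the same variance.

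**Equal SDs (k = 1).** The CI ratio is the square root of the variance ratio times the t quantile on N−3 df over that on N−2 df. The power column applies where the change-score test has 80%.

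| rho | V_a/V_c, N=32 | 95% CI width ratio, N=32 | Power after adjustment, N=32 | V_a/V_c, N=24 |
|---|---|---|---|---|
| 0 (limit) | 0.518 | 0.721 | – | 0.525 |
| 0.3 | 0.673 | 0.822 | 92.6% | 0.683 |
| 0.5 | 0.777 | 0.883 | 88.8% | 0.788 |
| 0.7 | 0.880 | 0.940 | 84.7% | 0.892 |
| 0.9 | 0.984 | 0.993 | 80.5% | 0.997 |
| 0.95 | 1.010 | 1.006 | 79.5% | 1.024 |

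With k = 1 the ratio is (1 + rho)/2 × (N−3)/(N−4). It reaches 1 at rho = (N−5)/(N−3): 27/29 = 0.931 for N=32 and 19/21 = 0.905 for N=24. For CI width the break-even points are slightly lower, about 0.925 and 0.894.

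**Unequal SDs, N = 32.**

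| k | rho 0.3 | rho 0.5 | rho 0.7 |
|---|---|---|---|
| 1.25 | 0.812 | 0.925 | 1.016 |
| 0.8 | 0.520 | 0.592 | 0.650 |

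**Largest possible loss.** Before the small-sample factor, V_c − V_a = 1 + k² − 2·rho·k − k²(1 − rho²) = (1 − rho·k)², which is never negative. The ratio therefore cannot exceed 1 + 1/(N−4), reached when rho·k = 1: 1.036 at N=32 and 1.050 at N=24.

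**Simulation check** (bivariate normal, 1:1). With 40,000 trials per setting, variance ratios agreed with the formula to within about 0.01 and both estimators were unbiased. In a separate run of 20,000 trials per setting with equal SDs, type I error was 0.048 to 0.054 across the two methods.

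**The case against.** The strongest reply is that nothing here is an error. A t-test on change is a legitimate randomised comparison, and it matches both Hypothesis 3, which is about attenuating a change, and the delta used in Aim 2. That is true. However, the linear model targets the same arm difference, so the hypothesis is unaffected and only the precision differs.

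Second, the size of the gain is unknown. This stands. Rho, the SDs and the allocation ratio are not in the documents, and the cases above run from a 48% variance cut to a 2.4% loss. The rho = 0 row is a limit, since it would mean that the first scan says nothing about the same person's second scan. At rho 0.9 with 24 participants the 95% CI would be about 0.2% wider.

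Third, the gap between scans is itself unclear. Section V, 3.A puts the baseline about a week before infusion, whereas the schedule in Section V, 3.F labels the three sessions Day-0, Day #1 and Day #2, which suggests the day before. A shorter gap could raise rho and shrink the gain. The scan precedes both drugs on either reading, so it remains a proper covariate.

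Fourth, Section V, 12 does not say whether Aim 3 is tested by voxel, by region or on one summary. By voxel there is no single rho: some voxels would gain and others could lose slightly. The CI, power and 41-participant figures are therefore illustrations for one scalar outcome.

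The reference to an earlier report for GBC processing does not settle the point, because the plan states the Aim 3 group test itself. The 24-versus-32 conflict is a separate matter and the conclusion is the same under either total.

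**Conclusion.** The concern holds as a point about efficiency, not validity. The planned Aim 3 test ignores a pre-drug measurement that could be used as a covariate at almost no cost. With equal SDs and N=32, adjustment would cut the variance by roughly a tenth to a third for rho between 0.7 and 0.3, by little near 0.9, and not at all above about 0.93. A follow-up SD larger than baseline moves the break-even lower; a smaller one increases the gain. The possible loss is capped at 3.6% (N=32) or 5.0% (N=24). With rho undocumented, that asymmetry makes adjustment the better prespecified default. The percentages rest on the assumed rho, SD ratio and 1:1 allocation. The change should be made, but the trial does not fail without it.

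**What to change.** In Section V, 12, replace the Aim 3 t-test with a linear model of 24-hour GBC on arm and the participant's own baseline GBC at the same voxel or region. Report the adjusted arm difference with its 95% CI. Using delta GBC as the outcome in this model gives the same arm effect, so delta can stay for description and for the Aim 2 correlation. Fix the model, and the voxel set or region it applies to, before GBC is examined by arm.

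The same model may be used for the 3T secondary outcomes that have a pre-drug baseline. For very stable anatomical measures such as cortical thickness and volumes the gain may be nil. Do not apply it to glutamate, glutamine or GABA from MRS: their baseline follows the randomised tablet and may already reflect it.

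The cost is a revised sentence and one degree of freedom. A voxel-wise test would also need each participant's baseline GBC map entered as a voxel-specific covariate. No new data are needed, and delta GBC already requires both scans.
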